#### 4.1.4 Safety Assessment Period - Safety run-in:

The safety assessment period for DLT assessment encompasses 3 cycles of study treatment (i.e. 7 weeks total). Three weeks will be given for seroconversion following the first dose of talimogene laherparevec ( $4 \times 10^6$  pfu). Subsequent doses of talimogene laherparevec ( $4 \times 10^8$  pfu) will be given alone or with nivolumab (240 mg IV) every two weeks starting on Cycle 2, Day 1 for up to 8 cycles of therapy. Patients will be assessed for DLTs after seroconversion and 2 cycles of talimogene laherparevec given alone or with nivolumab every 2 weeks. Cohorts will be enrolled according to 3+3 rules and each subject must complete the safety assessment period before the next patient is treated (see above [study schema](#)). If  $\geq 2$  patients experience DLT in a dose cohort, the study will be discontinued.

## 4.2 Study Treatments

Agent	Pre-medications	Dose/Frequency	Route	Schedule
talimogene laherparevec (1 st dose only) 	30 min prior to IP talimogene laherparevec give anti-pyretic & anti-nausea meds (e.g., 500 mg	$4 \times 10^6$ pfu; next dose of talimogene laherparevec given 3 weeks later	via pleurX catheter and allow product to dwell for at least 24 hours	D1 cycle 1 only; subsequent dose given three weeks later
talimogene laherparevec (Subsequent doses) 	acetaminophen & 10 mg prochlorperazine)	$4 \times 10^8$ pfu every 2 weeks X 8 doses	via pleurX catheter and allow product to dwell for at	D1 cycle 2 of study for up to 8 cycles given every 2 weeks (14 days)

			least 24 hours	until fluid stops re-accumulating (i.e., resolution of pleural effusion) or until systemic disease progression
Nivolumab	See section 4.3.3 for management of infusion-related reactions associated with nivolumab	240 mg every 2 weeks	IV over 30 minutes	Starting on D1 of Cohort 2 Dose Level 2 and beyond; Every 2 weeks (14 days) until disease progression (per RECIST or irRC) or withdrawal for other reasons

1. [See Appendix D](#) -Information Sheet for Caregivers, Family Members or other Close Contacts to Clinical Trial Participants being given Talimogene Laherparepvec).

Talimogene laherparepvec (4 mL) at a concentration of  $10^6$  (1 million) plaque-forming units (pfu)/mL will be administered into the pleurX catheter for a total dose of  $4 \times 10^6$  pfu for the first dose. Subsequently, talimogene laherparepvec (4 mL) at a concentration of  $10^8$  (100 million) pfu/mL will be administered every two weeks into the pleurX catheter. Dosing with talimogene laherparepvec will be continued until pleural fluid stops re-accumulating or until systemic disease progression. Subjects who have resolution of pleural effusion as defined by the primary endpoints may continue nivolumab monotherapy per standard of care until disease progression. The dose rationale for talimogene laherparepvec therapy is based on the OPTiM trial in melanoma and subsequent analysis [44, 61].

All IP infusions of talimogene laherparepvec will be in 200cc NS followed by 20cc of sterile saline to flush the catheter. Subjects will be instructed to allow the product to dwell for at least 24 hours after which they should next drain the catheter when next needed to palliate shortness of breath, consistent with standard of care use of the catheter. Subjects or their caregivers will be instructed to use medical gloves when draining the catheter and to avoid physical contact with fluid drained from the catheter. Standard drainage bottles will be used. Subjects will be allowed to either add bleach to the bottle then dispose per standard procedures or return to the investigators for disposal. These precautions will be advised permanently after study initiation (See [Appendix D](#) -Information Sheet for Caregivers, Family Members or other Close Contacts to Clinical Trial Participants being given Talimogene Laherparepvec).

Nivolumab 240 mg will be administered (per standard of care) as a 30-minute IV infusion on D1 of each cycle every two weeks.

Nivolumab and talimogene laherparepvec may be administered in either order. Administration of the two agents should be within 30 hours of each other.

### 4.3 Dose Modifications/Delays

#### 4.3.1 Talimogene laherparepvec Dose Modifications/Delays

There will be no dose modifications allowed for talimogene laherparepvec during the study. Talimogene laherparepvec will be administered as described in section 4.2 above. Talimogene laherparepvec administration will either be withheld or permanently discontinued depending on the severity of event related to its administration. If a grade 4 DLT occurs, talimogene laherparepvec will be permanently discontinued. If grade 3 DLTs occur with talimogene laherparepvec administration as described in section 4.1.2 (Definition of DLTs), the next dose of talimogene laherparepvec will be withheld and will not be given until symptoms have resolved to  $\leq$  grade 1. If  $> 1$  scheduled dose of talimogene laherparepvec is missed due to toxicity, talimogene laherparepvec will be permanently discontinued.

Doses up to 4 mL at dose strength of  $10^8$  pfu/mL every 2 weeks (maximum cumulative dose of  $222.5 \times 10^8$  pfu) have been administered in clinical studies, with no evidence of DLT. The maximum cumulative dose of talimogene laherparepvec planned for this trial is 9 total administrations (including initial seroconversion dose). See section 5.1.6, for warnings and precautions related to talimogene laherparepvec administration. Patients may receive premedication with an anti-pyretic and anti-nausea medication (e.g., acetaminophen 500mg PO and prochloraperizine 10mg PO) prior to every talimogene laherparepvec injection.

#### 4.3.2 Nivolumab Dose Modifications/Delays

Toxicity grades per NCI-CTCAE Criteria v5.0

Adverse Reaction	Severity	Dose Modification
Colitis	Grade 2 diarrhea or colitis	Withhold dose a
	Grade 3 diarrhea or colitis	Withhold dose a when administered as a single agent
		Permanently discontinue when administered with ipilimumab
	Grade 4 diarrhea or colitis	Permanently discontinue
Pneumonitis	Grade 2 pneumonitis	Withhold dose a
	Grade 3 or 4 pneumonitis	Permanently discontinue
Hepatitis/non-HCC b	Aspartate aminotransferase (AST)/ or alanine aminotransferase (ALT) more than 3 and up to 5 X the ULN or total bilirubin $> 1.5$ and up to 3X ULN	Withhold dose a
	AST or ALT more than 5X ULN or total bilirubin $> 3X$ ULN	Permanently discontinue
Hepatitis/HCC b	If AST/SLT is within normal limits at baseline and increases to more than 3 and up to 5 times the ULN or total bilirubin more than 1.5 and up to 3 times the ULN	Withhold dose c
	If AST/ALT is more than 1 and up to 3	

	times ULN at baseline and increases to more than 5 and up to 10 times the ULN  If AST/ALT is more than 3 and up to 5 times ULN at baseline and increases to more than 8 and up to 10 times ULN	
	If AST/ALT is more than 3 and up to 5 times ULN at baseline and increases to more than 8 and up to 10 times the ULN	Permanently discontinue
Hypophysitis	Grade 2 or 3 hypophysitis	Withhold dose a
	Grade 4 hypophysitis	Permanently discontinue
Adrenal insufficiency	Grade 2 adrenal insufficiency	Withhold dose a
	Grade 3 or 4 adrenal insufficiency	Permanently discontinue
Type 1 Diabetes Mellitus	Grade 3 hyperglycemia	Withhold dose a
	Grade 4 hyperglycemia	Permanently discontinue
Nephritis and Renal Dysfunction	Serum creatinine more than 1.5 and up to 6X ULN	Withhold dose a
	Serum creatinine more than 6X ULN	Permanently discontinue
Skin	Grade 3 rash or suspected Stevens-Johnson syndrome (SJS) or toxic epidermal necrolysis (TEN)	Withhold dose a
	Grade 4 rash or confirmed SJS or TEN	Permanently discontinue
Encephalitis	New-onset moderate or severe neurologic signs or symptoms	Withhold dose a
	Immune-mediated encephalitis	Permanently discontinue
Other	Other Grade 3 adverse reaction First occurrence	Withhold dose a
	Recurrence of same Grade 3 adverse reaction	Permanently discontinue
	Life-threatening or Grade 4 adverse reaction	Permanently discontinue
	Grade 3 myocarditis	Permanently discontinue
	Requirement for 10 mg per day or greater prednisone or equivalent for more than 12 weeks	Permanently discontinue
	Persistent Grade 2 or 3 adverse reactions lasting 12 weeks or longer	Permanently discontinue

- a) Resume treatment when adverse reaction returns to Grade 0 or 1.
- b) HCC: hepatocellular carcinoma
- c) Resume treatment when AST/ALT returns to baseline.

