## 3.0 PATIENT ELIGIBILITY

### 3.1 Inclusion Criteria

Patients must meet all of the following inclusion criteria to participate in this study:

- 3.1.1 Signed a written IRB-approved informed consent and HIPAA authorization for the trial.
- 3.1.2 Be  $\geq 18$  years of age on day of signing informed consent.

- 3.1.3 ECOG Performance Status  $\leq 2$ . (See Appendix A: ECOG Performance Status).
- 3.1.4 Histologically or cytologically confirmed stage IV metastatic cancer.
- 3.1.5 Confirmation of malignant pleural effusion via imaging (CXR, CT scan, ultrasound, MRI, or PET/CT) and cytology for which pleurX catheter placement is standard of care.
- Dose Level 1: Either no systemic therapy available per standard of care, or delay in administration of systemic therapy considered clinically acceptable.
  - Dose Level 2/Phase II: Nivolumab alone would be an acceptable standard treatment OR have a tumor type with prior data for PD1 efficacy OR non-pleural disease is not considered a significant risk to the patient OR refractory to standard therapies.
- 3.1.6 Demonstrate adequate organ function as defined in the table below. All screening labs should be performed within 14 days of treatment initiation.

System	Laboratory Value 
Hematological	
Absolute neutrophil count (ANC)	$\geq 1000 /\mu\text{L}$
Platelets	$\geq 50,000 / \mu\text{L}$
Hemoglobin	$\geq 10 \text{ g/dL}$ (acceptable to reach this through transfusion)
Renal	
Calculated creatinine clearance (Cockcroft-Gault) 	$\geq 45 \text{ mL/min}$
Coagulation	
INR or PT	$\leq 1.5 \times \text{ULN}$ unless the subject is receiving anticoagulant therapy, in which case PT and PTT/aPTT must be within therapeutic range of intended use of anticoagulants
Hepatic	
Serum total bilirubin	$\leq 1.5 \times \text{ULN}$ OR Direct bilirubin $\leq \text{ULN}$ for subjects with total bilirubin levels $> 1.5 \text{ ULN}$
AST (SGOT) and ALT (SGPT)	$\leq 2.5 \times \text{ULN}$ OR $\leq 5 \times \text{ULN}$ for subjects with liver metastases
Albumin	$> 2.5 \text{ mg/dL}$
Pulmonary	
Pulse Oximetry	At least 90% on room air ( OR 95% on oxygen)
Cardiac	
EKG	No clinically relevant cardiac dysfunction
Troponin	$< 0.3$

System	Laboratory Value 
--------	-------------------------------

[figure not shown]
1. See [Appendix B](#) (Section 11.2) for Cockcroft-Gault formula.

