  2. Hematology and other lab parameters that are  $\leq$  grade 2 BUT still meet criteria for study entry are allowed. Furthermore, changes in laboratory parameters during the study should not be considered adverse events unless they meet criteria for dose modification(s) of study medication outlined by the protocol and/or worsen from baseline during therapy.
- 3.1.7 Recovered from all reversible toxicities related to their previous treatment (other than alopecia) to  $\leq$  grade 1 or baseline; exceptions to this criterion may be allowed following review by the principal investigator for toxicities that are not expected to be exacerbated by nivolumab or talimogene laherparepvec. Grade 2 peripheral neuropathy will not result in exclusion as neither study agent would be expected to exacerbate it.
- 3.1.8 No history of untreated brain metastasis. Treated brain metastases must not be known to be progressive, symptomatic, or currently requiring  $> 10$  mg of prednisone or prednisone equivalents within two weeks prior to study drug administration.
- 3.1.9 Females of childbearing potential must have a negative serum pregnancy test within 72 hours prior to receiving the first dose of study medication. Females of childbearing potential must agree to use 2 methods of effective contraception or abstain from heterosexual sex throughout the treatment period and for 5 months after the last dose of study treatment. Females of childbearing potential are women who have not been surgically sterilized (have undergone a hysterectomy, bilateral tubal ligation, or bilateral oophorectomy) or have not been free of menses for  $>1$  year.
- 3.1.10 Male patients with female partners must have had a prior vasectomy or agree to use an adequate method of contraception (i.e. double barrier method: condom plus spermicidal agent) starting with the first dose of study therapy through 7 months after the last dose of study treatment.
- 3.1.11 As determined by the enrolling physician or protocol designee, ability or willingness of the patient to understand and comply with study procedures.
- 3.2 Exclusion Criteria**
- Patients meeting any of the following exclusion criteria will not be able to participate in this study:
- 3.2.1 Receiving any investigational agent, or using an investigational device, currently or within 28 days or 5 half-lives of Day 1 of treatment on this study, whichever is longer.

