**Nivolumab administration should be delayed for the following:**

Any Grade  $\geq 2$  non-skin, drug-related AE, with the following exceptions:

- Grade 2 drug-related fatigue or laboratory abnormalities do not require a treatment delay
- Any Grade 3 skin, drug-related AE

Any Grade 3 drug-related laboratory abnormality, with the following exceptions for lymphopenia, leukopenia, AST, ALT, total bilirubin, or asymptomatic amylase or lipase:

- Grade 3 lymphocyte count decreased or white blood cell decreased does not require dose delay.
- If a subject has a baseline AST, ALT, or total bilirubin that is within normal limits, delay dosing for drug-related Grade  $\geq 2$  toxicity.
- If a subject has baseline AST, ALT, or total bilirubin within the Grade 1 toxicity range, delay dosing for drug-related Grade  $\geq 3$  toxicity.
- Any Grade  $\geq 3$  drug-related amylase or lipase abnormality that is not associated with symptoms or clinical manifestations of pancreatitis does not require dose delay. The Investigator should be consulted for such Grade  $\geq 3$  amylase or lipase abnormalities.

Any AE, laboratory abnormality, or intercurrent illness that, in the judgment of the investigator, warrants delaying the dose of study medication.

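### The nivolumab table assigns two incompatible actions to one AST/ALT rise in hepatocellular carcinoma, and its liver limits disagree with other sections of the protocol

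*Combined protocol and SAP*

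**What the plan says.** **HCC rows, section 4.3.2 table.** The withhold block lists three baseline-dependent AST/ALT conditions:

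- normal at baseline, rising to above 3 and up to 5 x ULN;
- above 1 and up to 3 x ULN at baseline, rising to above 5 and up to 10 x ULN;
- AST/ALT that "is more than 3 and up to 5 times ULN at baseline and increases to more than 8 and up to 10 times ULN".

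Footnote c applies to the block: "Resume treatment when AST/ALT returns to baseline". The next HCC row carries permanent discontinuation. It has the same baseline band as the third condition and the same rise: "increases to more than 8 and up to 10 times the ULN".

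**Non-HCC rows, same table.** Nivolumab is withheld for AST/ALT "more than 3 and up to 5 X the ULN or total bilirubin" above its own limit, and permanently discontinued above 5 x ULN. Neither row mentions baseline. Footnote a governs resumption: "Resume treatment when adverse reaction returns to Grade 0 or 1".

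**Entry, section 3.1.6.** AST/ALT must be at most 2.5 x ULN, or at most 5 x ULN "for subjects with liver metastases". Footnote 2 adds that laboratory values up to grade 2 that "BUT still meet criteria for study entry are allowed".

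**Other nivolumab rules.**

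- Section 4.3.2.1 limits the delay criteria to drug-related events. By default it delays dosing for a Grade 3 drug-related laboratory abnormality, with liver exceptions for a normal baseline (delay from Grade 2) and for a Grade 1 baseline: "If a subject has baseline AST, ALT, or total bilirubin within the Grade 1 toxicity range, delay dosing for drug-related Grade" 3 or higher.
- Section 4.3.2.2 allows resumption at Grade 1 or lower, or at the baseline value.
- Section 4.3.2.4 requires discontinuation for a drug-related AST or ALT above 8 x ULN.
- The hepatic algorithm in Appendix C has a note allowing delay in place of discontinuation up to 8 x ULN.

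**The concern.** A dose-modification table is useful only if a given laboratory value leads to one action. Here an HCC patient with a qualifying baseline and a value of 9 x ULN is told both to pause with a route back to treatment and to stop for good. For non-HCC patients the table, the delay criteria, the discontinuation criteria and the appendix set different limits. Only some of them take account of the raised baseline that the entry criteria permit.

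At stake are patient safety and uniform handling of a drug for which section 5.2.8 lists immune-mediated hepatitis. Everyone treated at dose level 2 enters the safety and efficacy analyses (sections 4.1.1 and 8.1), so nivolumab exposure in that set could depend on which line a site happens to read.

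**Working it through.** The plan states no figure to reproduce. The check compares the printed ranges. Let *b* be baseline and *v* the on-treatment AST/ALT, both in multiples of ULN.

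**Step 1: HCC, table against itself.**

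- Third withhold condition: 3 < *b* ≤ 5 and 8 < *v* ≤ 10.
- Discontinuation row: 3 < *b* ≤ 5 and 8 < *v* ≤ 10.

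The intersection is the whole region. At *b* = 4 or 5, values of 8.5, 9 and 10 each fall in both rows.

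**Step 2: HCC, table against section 4.3.2.4 (*v* > 8, drug-related).**

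| Baseline *b* | Value *v* | Table | Section 4.3.2.4 |
|---|---|---|---|
| 2 | 6, 8 | withhold | not met |
| 2 | 8.5, 9, 10 | withhold | discontinue |
| 4 | 8.5, 9, 10 | withhold and discontinue | discontinue |
| 2 or 4 | 11 | no row | discontinue |

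The conflict therefore also touches the second withhold condition (1 < *b* ≤ 3, 5 < *v* ≤ 10) in its part above 8. A baseline of 2 meets the ordinary 2.5 x ULN entry limit. Above 10 x ULN the gap is in the table only, because section 4.3.2.4 supplies an action if the rise is drug-related.

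**Step 3: non-HCC, table against entry.** Baselines of 2.5 and 3.0 lie outside the withhold band. Baselines of 3.01, 4 and 5 lie inside it, and all are eligible with liver metastases. The part of the entry range above 3 x ULN is thus numerically the same interval as the withhold band.

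**Step 4: non-HCC, table against the other rules**, for an isolated drug-related AST/ALT rise (no concurrent bilirubin criterion):

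| Value *v* | 4.3.2 table | 4.3.2.4 | Appendix C note |
|---|---|---|---|
| above 3 to 5 | withhold, any baseline | not met | delay allowed in place of stopping |
| above 5 to 8 | permanently discontinue | not met | delay allowed in place of stopping |
| above 8 | permanently discontinue | discontinue | outside the delay allowance |

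The stop rules disagree over the whole band above 5 and up to 8 x ULN. As an illustration, a patient who enters at 4.9 and reaches 5.1, judged drug-related, has moved by 5.1 − 4.9 = 0.2 x ULN. The table stops nivolumab permanently; section 4.3.2.4 does not, since 5.1 is below 8.

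Section 4.3.2.1 works in grades. The protocol does not print grade limits as multiples of ULN, so no conversion is made. A Grade 1 baseline leads to delay at Grade 3 or higher by the specific bullet. A higher baseline has no bullet and falls under the general Grade 3 rule. Neither reads as a fixed 3 x ULN trigger.

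**Step 5: resumption.** Footnote a requires Grade 0 or 1; section 4.3.2.2 also accepts the baseline value. If an eligible baseline is above Grade 1 (assumption, for the reason just given), a patient back at baseline may resume under section 4.3.2.2 but not under footnote a. Interruption beyond 6 weeks generally means permanent discontinuation (sections 4.3.2.2 and 4.3.2.4, with exceptions), so this difference could decide whether treatment ends.

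**The case against.** The strongest reply is that this is a copying slip in a rarely used row, and that other sections fill most of the holes. Much of that stands.

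- *The withhold action is inferred.* In the available text the first printing of the condition has no action beside it; the action comes from a merged cell that runs over a page break. Withholding is still the natural reading, since otherwise the entry has no action or is a bare duplicate.
- *Few patients reach it.* A baseline above 3 x ULN is admissible only under the liver-metastases limit. Section 3.2.14 excludes known hepatitis C and active hepatitis B, and section 3.2.16 excludes active hepatic disease apart from listed exceptions such as stable chronic liver disease. HCC itself is not named as an exclusion.
- *Section 4.3.2.1 has a default.* A reader might infer that it is silent for baselines above Grade 1. It is not: the normal and Grade 1 bullets are exceptions to a general Grade 3 rule.

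A reader might also infer from Step 3 that an eligible patient at 4 x ULN must have the first nivolumab dose withheld. The documents do not support that. The table's first column is headed as adverse reactions, the row is hepatitis, and the delay criteria concern drug-related events. A stable elevation that precedes any nivolumab is not clearly either. What remains is on-treatment ambiguity: under section 3.1.6 footnote 2 a laboratory change can count as an adverse event once it meets dose-modification criteria or worsens from baseline.

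Nothing in these replies removes the duplicated condition, the 8 to 10 x ULN conflict, the 5 against 8 x ULN difference, or the two resumption rules.

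**Conclusion.** The point holds as an internal contradiction in the safety instructions.

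- **HCC:** one condition carries two incompatible actions over its entire range, and the withhold entries conflict with section 4.3.2.4 between 8 and 10 x ULN.
- **Non-HCC:** the table has no baseline reference although entry allows up to 5 x ULN with liver metastases. It differs from section 4.3.2.4 and Appendix C above 5 and up to 8 x ULN, and from section 4.3.2.1 in how delay is triggered. Its footnote a differs from section 4.3.2.2 on resumption.

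This rests on two readings: that the merged cell extends the withhold action to the first printing, and that the rises are judged drug-related. The hepatic flow chart in Appendix C is not visible in the available text, so only its note was used.

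It is tempting to carry this through to the 15-of-24 rejection rule by supposing that some of the 24 lose nivolumab. The documents give no count of patients with such baselines, and the route through a withheld first dose is not established. The sample size and the primary test are unaffected.

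**What to change.** The sponsor's clinical team should reconcile the section 4.3.2 table and its footnotes a and c with sections 3.1.6, 4.3.2.1, 4.3.2.2 and 4.3.2.4 and the hepatic algorithm in Appendix C. The revised text should meet four tests:

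1. no HCC condition appears under two actions, and values above 10 x ULN have an entry or a cross-reference;
2. the non-HCC rows state how they apply to a patient admitted above 3 and up to 5 x ULN;
3. one resumption rule applies to each row;
4. where sections differ, the text says which one governs.

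Which thresholds apply is a clinical decision and is not addressed here.

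The cost is a text amendment, with the manufacturer review and IRB approval that section 9.6 requires. Visits, data collection, sample size and the analysis do not change.

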#### 4.3.2.1 Dose Delay Criteria for Nivolumab

Because of the potential for clinically meaningful nivolumab-related AEs requiring early recognition and prompt intervention, management algorithms have been developed for suspected AEs of selected categories [see [Appendix C](#) section 11.3].

Dose delay criteria apply for all drug-related AEs. Nivolumab must be delayed until treatment can resume.

